## Table 7: Dose Modification Guidelines for Pembrolizumab

#### Instructions:

- 1. Corticosteroid taper should be initiated upon AE improving to Grade 1 or less and continue to taper over at least 4 weeks.
- 2. For situations where pembrolizumab has been withheld, pembrolizumab can be resumed after AE has been reduced to Grade 1 or 0 and corticosteroid has been tapered. Pembrolizumab should be permanently discontinued if AE does not resolve within 12 weeks of last dose or corticosteroids cannot be reduced to ≤10 mg prednisone or equivalent per day within 12 weeks.
- **3.** For severe and life-threatening irAEs, IV corticosteroid should be initiated first followed by oral steroid. Other immunosuppressive treatment should be initiated if irAEs cannot be controlled by corticosteroids.

Immune-related AEs	Toxicity grade or conditions (CTCAEv5.0)	Action taken to pembrolizumab	irAE management with corticosteroid and/or other therapies	Monitor and follow-up
Pneumonitis	See Table 4	See Table 4	See Table 4	See Table 4

NCI Protocol #: N/A DF/HCC Protocol #: 18-602 rsion Date: December 11, 2023

			Protocol	Version Date: December 11, 2
Diarrhea / Colitis	Grade 2 or 3 Withhold	
 
Administer corticosteroids (initial dose of 1- 2 mg/kg prednisone or equivalent) followed by
 
	Monitor     participants for     signs and     symptoms of     enterocolitis (ie,     diarrhea,     abdominal pain,	
		discontinue	taper	
 
blood or mucus in stool with or without fever) and of bowel perforation (ie, peritoneal signs and ileus).
 
Participants with ≥ Grade 2 diarrhea suspecting colitis should consider GI consultation and performing endoscopy to rule out colitis.
 
Participants with diarrhea/colitis should be advised to drink liberal quantities of clear fluids. If sufficient oral fluid intake is not feasible, fluid and electrolytes should be substituted via IV infusion.
 

AST / ALT elevation or Increased bilirubin	Grade 2	Withhold	Administer corticosteroids (initial dose of 0.5-1 mg/kg prednisone or equivalent) followed by taper	Monitor with liver function tests (consider weekly or more frequently until liver enzyme value returned to baseline or is
	Grade 3 or 4	Permanently discontinue	• Administer corticosteroids (initial dose of 1- 2 mg/kg prednisone or equivalent)	stable

NCI Protocol #: N/A DF/HCC Protocol #: 18-602 Protocol Version Date: December 11, 2023

			followed by taper	
Type 1 diabetes mellitus (T1DM) or Hyperglycemia	Newly onset T1DM or Grade 3 or 4 hyperglycemia associated with evidence of β-cell failure	Withhold	
 
Initiate insulin replacement therapy for participants with T1DM
 
Administer anti- hyperglycemic in participants with hyperglycemia
 
	• Monitor participants for hyperglycemia or other signs and symptoms of diabetes.
Hypophysitis	Grade 2	Withhold	Administer corticosteroids and initiate	• Monitor for signs and symptoms of
	Grade 3 or 4	Withhold or permanently discontinue 	hormonal replacements as clinically indicated.	hypophysitis (including hypopituitarism and adrenal insufficiency)
Hyperthyroidism	Grade 2	Continue	• Treat with non- selective beta- blockers (eg,	Monitor for signs and symptoms of
	Grade 3 or 4	Withhold or permanently discontinue 	propranolol) or thionamides as appropriate	thyroid disorders.
Hypothyroidism	Grade 2-4	Continue	• Initiate thyroid replacement hormones (eg, levothyroxine or liothyroinine) per standard of care	
 
Monitor for signs and symptoms of thyroid disorders.
 

Nephritis and Renal dysfunction	Grade 2	Withhold	Administer corticosteroids	Monitor     changes of
	Grade 3 or 4	Permanently discontinue	(prednisone 1-2 mg/kg or equivalent) followed by taper.	renal function
Neurological Toxicities	Grade 3 or 4	Permanently discontinue	• Based on severity of AE administer corticosteroids	Ensure     adequate     evaluation to     confirm     etiology and/or     exclude other     causes
Myocarditis	Grade 1	Withhold	Based on severity of AE administer	• Ensure adequate
	Grade 2, 3 or 4	Permanently discontinue	corticosteroids	evaluation to confirm etiology and/or exclude other

NCI Protocol #: N/A DF/HCC Protocol #: 18-602 Protocol Version Date: December 11, 2023

Exfoliative Dermatologic ConditionsSuspected SJS, TEN, or DRESSWithhold• Based on severity of AE administer continue• Ensure adequate evaluation to conticosteroids					causes
etiology or exclude other causes	foliative rmatologic nditions	re Suspected SJS, TEN, or DRESS Is Confirmed SJS, TEN, or DRESS	Withhold Permanently discontinue	Based on severity of AE administer corticosteroids	Ensure adequate evaluation to confirm etiology or exclude other causes
All other immune- related AEsIntolerable/ persistent Grade 2Withhold• Based on type and severity of AE administer corticosteroids• Ensure adequate evaluation to confirm etiology and/o exclude other causesAll other immune- related AEsIntolerable/ persistent Grade 2Withhold or discontinue based on the type of event. Events that require discontinuation include and not limited to: Gullain- Barre Syndrome, encephalitis• Based on type and severity of AE administer corticosteroids• Ensure adequate evaluation to confirm etiology and/o exclude other causes	l other immune- ated AEs	immune- Es Intolerable/ persistent Grade 2 Grade 3	Withhold or discontinue based on the type of event. Events that require discontinuation include and not limited to: Gullain- Barre Syndrome, encephalitis	Based on type and severity of AE administer corticosteroids	Ensure adequate evaluation to confirm etiology and/or exclude other causes
Grade 4 or recurrent Permanently discontinue		Grade 4 or recurrent Grade 3	Permanently discontinue		

1. Withhold or permanently discontinue pembrolizumab is at the discretion of the investigator or treating physician.

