## 5.2.2 Subsequent Cycles

- Absolute neutrophil count  $\geq$ 1,000/mcL
- Platelets  $\geq$ 75,000/mcL
- AST (SGOT) / ALT (SGPT)  $\leq 2.5$  x institutional upper limit of normal
- Creatinine ≤ institutional upper limit of normal or creatinine clearance >= 40 mL/min/1.73 m2 for subjects with creatinine levels above institutional normal
- All toxicities pf previous cycles must have resolved to  $\leq$  grade 2
- ECOG performance of 0 to 2
- No evidence of life-threatening medical problems

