### Attribution of Toxicity:

When study interventions are administered in combination, attribution of an adverse event to a single component is likely to be difficult. Therefore, while the investigator may attribute a toxicity event to the combination, to mirvetuximab soravtansine alone or to pembrolizumab alone, for adverse events listed in Table 7, both interventions must be held according to the criteria in Table 7 Dose Modification Guidelines for Pembrolizumab.

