#### 6.3 **Re-treatment Criteria**

For a patient to begin a new cycle or continue a cycle of therapy after a dose modification, the following criteria must be met.

- Pre-treatment criteria as described in Section 5.2.2 with the following exceptions
  - $\circ$  Treatment-emergent ocular disorders, which must have recovered to  $\leq$  Grade 1 or baseline
  - $\circ$  Treatment-emergent pneumonitis which must have recovered to  $\leq$  Grade 1

If the patient does not meet these criteria, dosing with the two agents in the combination regimen will be delayed and the patient should be re-evaluated within 48-72 hours. Dosing with both agents may resume if these criteria have been met. If the adverse event can be attributed to one of the agents in the combination regimen, that agent will be held or discontinued as per the Dose Modification Guidelines

described in Sections 6.1 and 6.2 respectively; however, treatment with the second agent may resume provided all the other criteria are met. However, if the next cycle is delayed due to treatment-related toxicity longer than 12 weeks then the patient should be removed from study treatment. In such cases, continuation of study treatment may be considered for those patients who have experienced clinical benefit if agreed upon between the Overall PI and the Investigator.

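### Section 6.3 can be read as letting both agents resume at Grade 2 or less with no steroid condition, while Table 7 holds pembrolizumab until Grade 1 or 0 after a taper, and no order of precedence is given

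*Combined protocol and SAP*

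**What the plan says.** Table 7 (Section 6.2), instruction 2, states that where it has been withheld, "pembrolizumab can be resumed after AE has been reduced to Grade 1 or 0 and corticosteroid has been tapered". Instruction 1 has the taper last at least 4 weeks.

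Section 6.3 lists what must be satisfied to start a new cycle or to continue after a dose modification: "Pre-treatment criteria as described in Section 5.2.2 with the following exceptions". Section 5.2.2 reads "All toxicities pf previous cycles must have resolved to" Grade 2 or less. Section 6.3 has two exceptions:
- "Treatment-emergent ocular disorders, which must have recovered to" Grade 1 or less, or baseline.
- "Treatment-emergent pneumonitis which must have recovered to" Grade 1 or less.

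If the criteria are not met, both agents are delayed and the patient is re-evaluated. Then: "Dosing with both agents may resume if these criteria have been met". Neither 5.2.2 nor 6.3 mentions a corticosteroid taper.

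On attribution, 6.3 says: "If the adverse event can be attributed to one of the agents in the combination regimen, that agent will be held or discontinued as per" Sections 6.1 and 6.2, and the second agent may restart if its other criteria are met. Section 6.2, under Attribution of Toxicity, recognises that blame is hard to assign to one component. It directs that for Table 7 events, "both interventions must be held according to the criteria in Table 7 Dose Modification Guidelines for Pembrolizumab". The next paragraph, on holding study interventions, repeats that both are held when an event is considered immune-related.

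**The concern.** A patient can meet the resumption rule in one section while another section still bars one of the two drugs. The trial is multi-center (Appendix B), so two sites could handle the same event differently and each cite the protocol. At stake are the safety of checkpoint-inhibitor re-challenge, the consistency of exposure between sites, and the reading of the toxicity results, which are a secondary objective (Section 1.3). The documents do not show how large any of these effects would be.

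**Working it through.** The plan states no figure to reproduce. The check compares the rules side by side.

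| Condition | Section 6.3 via 5.2.2 | Table 7, instructions 1 and 2 |
|---|---|---|
| Grade at which pembrolizumab may resume | 2 or less (1 or less for ocular events and pneumonitis) | 1 or 0 |
| Corticosteroid | no condition | tapered, over at least 4 weeks |
| Delay or non-resolution past 12 weeks | removal, but continuation possible by agreement if there is clinical benefit | pembrolizumab permanently discontinued if the event has not resolved |

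**Size of the gap.** 2 − 1 = 1 CTCAE grade, plus the taper condition.

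**Worked case.** Take Grade 2 colitis attributed to the combination, with the patient still on prednisone and every other 5.2.2 item met. Table 7 withholds pembrolizumab at this grade. Colitis is not an exception in 6.3, so the Grade 2 limit is met and the sentence allowing both agents to resume applies. Table 7 still bars pembrolizumab on grade and on steroid. Section 5.4.3 does not settle it, because it allows systemic steroids for suspected immunologic events.

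**Where the conflict is clear** (attributed to the combination, or not attributable to one agent):
- Grade 2 colitis, as above.
- Grade 2 bilirubin rise. Bilirubin has a limit in 5.2.1 but none in 5.2.2.
- Grade 2 hypophysitis. The note under Table 7 relaxes the resumption grade only for Grade 3 or 4 endocrinopathy, so Grade 2 onset stays under instruction 2.
- Intolerable or persistent Grade 2 events in the residual immune category.

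**Where it does not arise or is not shown:**
- Pneumonitis: 6.3 already requires Grade 1 or less.
- Grade 2 hyperthyroidism and Grade 2 to 4 hypothyroidism: Table 7 continues pembrolizumab.
- Grade 3 or 4 endocrinopathy: the note allows resumption at Grade 2 or less once controlled, the same grade as 5.2.2.
- Hepatic and renal events of Grade 3 or 4: permanently discontinued, so there is no resumption to dispute.
- Grade 2 AST/ALT and renal events: 5.2.2 has its own limits (AST/ALT at most 2.5 times the upper limit of normal; creatinine within normal, or clearance at least 40 mL/min/1.73 m²). Whether a Grade 2 case would pass them depends on CTCAE cut-points that Appendix C does not reproduce.
- Events attributed to pembrolizumab alone: 6.3 sends that drug back to Section 6.2, hence to Table 7.

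**Related contradictions.**
1. When an event is attributed to one agent, 6.3 lets the other restart. Section 6.2 holds both for Table 7 or immune-related events, whatever the attribution.
2. The 12-week provisions in the last row of the table lead to different outcomes for pembrolizumab.
3. Under Restarting Study Interventions in 6.2, the first bullet ends all study treatment if toxicity does not resolve. The second describes restarting the combination under that same circumstance.

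**The case against.** The best defence is that the rules add up. Section 6.3 is phrased as criteria that have to be met, so it can serve as a general gate on every cycle with Table 7 applying on top. Section 6.1.3 uses Section 5.2 in that way for mirvetuximab. Section 6.2 also anticipates unclear attribution by holding both agents under Table 7, and its restart paragraph points to Table 7 rather than 6.3. On this reading a patient needs both sets of conditions and there is no conflict.

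That reading is plausible, but three features of 6.3 count against relying on it. If the tables always controlled, the pneumonitis exception would be redundant, since Table 4 already requires Grade 1 or less; listing it invites the inference that unlisted immune events follow the Grade 2 limit. The sentence on resuming both agents is worded as sufficient. And on the second agent and on delays past 12 weeks, 6.3 permits what Section 6.2 and Table 7 exclude, so it is not simply an extra gate.

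The defence does succeed in narrowing the point. A reader might infer that every Grade 2 immune event is at once re-treatable and barred, or that Table 7 always demands Grade 1 or 0. The documents do not support either: the note under Table 7, the thyroid rows, the pneumonitis exception, the 5.2.2 laboratory limits and the attribution clause each remove cases.

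**Conclusion.** This is an internal contradiction in the re-treatment rules, not a disputable design choice, and it should be corrected. For the four kinds of Grade 2 event listed, when attributed to the combination or to neither agent alone, the text supports two answers that differ by one grade and a steroid taper, with no stated precedence. The conclusion rests on reading the 6.3 resumption sentence as sufficient. If the sponsor intends it only as a minimum, what remains on resumption grade and steroids is a missing precedence statement, but the disagreements on the second agent, on 12 weeks and between the two restart bullets still stand.

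The Grade 2 limit comes from 5.2.2; 6.3 only imports it. The documents give no expected frequency for these events, so the number of patients affected cannot be estimated. A reader might also infer that the two-stage design or its error rates are compromised; nothing in the documents shows that.

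**What to change.** Reconcile Section 5.2.2, the attribution, holding and restarting paragraphs of Section 6.2, Table 7 with its note on endocrinopathy, and Section 6.3. State in 6.3 which passage governs resumption of each agent after a Table 7 event, whatever the attribution, covering both the grade and the corticosteroid condition, and whether the same condition applies to mirvetuximab when both drugs were held. In the same edit, settle whether the second agent may restart, what follows a delay beyond 12 weeks, and the two bullets on unresolved toxicity. Which rule applies is for the medical lead.

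The cost is a wording change and cross-references in the next amendment, with no new data or visits.

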#### NOTE:

• For participants with Grade 3 or 4 immune-related endocrinopathy where withhold of pembrolizumab is required, pembrolizumab may be resumed when AE resolves to ≤ Grade 2 and is controlled with hormonal replacement therapy or achieved metabolic control (in case of T1DM).

Pembrolizumab may be interrupted for situations other than treatment-related AEs such as medical / surgical events or logistical reasons not related to study therapy. Participants should be placed back on study therapy within 3 weeks of the scheduled interruption, unless otherwise discussed with the Overall PI. The reason for interruption should be documented in the patient's study record.

#### 6.3 **Re-treatment Criteria**

For a patient to begin a new cycle or continue a cycle of therapy after a dose modification, the following criteria must be met.

- Pre-treatment criteria as described in Section 5.2.2 with the following exceptions
  - $\circ$  Treatment-emergent ocular disorders, which must have recovered to  $\leq$  Grade 1 or baseline
  - $\circ$  Treatment-emergent pneumonitis which must have recovered to  $\leq$  Grade 1

If the patient does not meet these criteria, dosing with the two agents in the combination regimen will be delayed and the patient should be re-evaluated within 48-72 hours. Dosing with both agents may resume if these criteria have been met. If the adverse event can be attributed to one of the agents in the combination regimen, that agent will be held or discontinued as per the Dose Modification Guidelines

described in Sections 6.1 and 6.2 respectively; however, treatment with the second agent may resume provided all the other criteria are met. However, if the next cycle is delayed due to treatment-related toxicity longer than 12 weeks then the patient should be removed from study treatment. In such cases, continuation of study treatment may be considered for those patients who have experienced clinical benefit if agreed upon between the Overall PI and the Investigator.

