## **Table 4: Management of Pneumonitis**

	CTCAE v5.0 Severity	Dose Modifications	irAE management	Monitor and follow-
--	---------------------	---------------------------	-----------------	---------------------

Grade		with corticosteroid and/or other therapies	up
Grade 1	Continue dosing after discussion with the Overall PI		
Grade 2	Withhold mirvetuximab soravtansine and pembrolizumab (both agents) Mirvetuximab soravtansine can be resumed at a dose reduced by one dosing level (see Table 6), and pembrolizumab can be resumed at same dosing level after discussion with the Overall PI when symptoms resolve to ≤ Grade 1	Administer corticosteroids (initial dose of 1-2 mg/kg prednisone or equivalent) followed by taper*	
 
Monitor participants for signs and symptoms of pneumonitis
 
Evaluate participants with suspected pneumonitis with radiographic imaging and initiate corticosteroid treatment
 
Add prophylactic antibiotics for opportunistic infections
 

Grade 3 or 4, or recurrent Grade 2	Permanently discontinue mirvetuximab soravtansine and pembrolizumab (both agents)	Administer corticosteroids (initial dose of 1-2 mg/kg prednisone or equivalent) followed by taper*	
 
Monitor participants for signs and symptoms of pneumonitis
 
Evaluate participants with suspected pneumonitis with radiographic imaging and initiate corticosteroid treatment
 
Add prophylactic antibiotics for opportunistic infections
 

\* Notes on steroids for irAE:

1. Corticosteroid taper should be initiated upon AE improving to Grade 1 or less and continue to taper over at least 4 weeks.

 Pembrolizumab and mirvetuximab soravtansine can be resumed after AE has been reduced to Grade 1 or 0 and corticosteroid has been tapered. Both agents should be permanently discontinued if AE does not resolve within 12 weeks of last dose or corticosteroids cannot be reduced to ≤10 mg prednisone or equivalent per day within 12 weeks.

**3.** For severe and life-threatening irAEs, IV corticosteroid should be initiated first followed by oral steroid. Other immunosuppressive treatment should be initiated if irAEs cannot be controlled by corticosteroids.

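### Section 6.3's 12-week re-treatment limit runs from a later start than the limits in Tables 4 and 7, has no steroid condition, and can be waived with no event excluded

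*Combined protocol and SAP*

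**What the plan says.** Section 6.3 sets the conditions for starting a new cycle. It imports the Section 5.2.2 list ("All toxicities pf previous cycles must have resolved to" Grade 2 or lower) and tightens it for lung events: "Treatment-emergent pneumonitis which must have recovered to" Grade 1 or lower. It then says "Dosing with both agents may resume if these criteria have been met". Neither list contains a steroid dose. A general time limit follows: "if the next cycle is delayed due to treatment-related toxicity longer than 12 weeks then the patient should be removed from study treatment". The waiver comes straight after it: "In such cases, continuation of study treatment may be considered for those patients who have experienced clinical benefit". One procedural condition is attached, namely that it applies only "if agreed upon between the Overall PI and the Investigator".

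Table 4 note 2, on pneumonitis, is stricter. On resumption it says "Pembrolizumab and mirvetuximab soravtansine can be resumed after AE has been reduced to Grade 1 or 0 and corticosteroid has been tapered". On stopping it says "Both agents should be permanently discontinued if AE does not resolve within 12 weeks of last dose or corticosteroids cannot be reduced"; the steroid target is 10 mg/day prednisone equivalent or less, to be reached within 12 weeks. Table 7 instruction 2 applies the same stop rule to pembrolizumab for the other listed immune-related events. Neither table gives an exception.

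Section 6.2 (Restarting Study Interventions) has two bullets that bear on this. The first requires every study drug to be stopped if the toxicity does not resolve or the resumption criteria are not met. The second, as printed, lets the combination restart at the investigator's discretion when toxicities have not resolved but the Table 7 conditions are satisfied.

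**The concern.** Both rules use 12 weeks, but they start from different points, and only the tables look at steroid dose. Only Section 6.3 has a waiver, and nothing in it holds back the events for which the tables call for permanent discontinuation. An investigator working from Section 6.3 could therefore re-dose both drugs after a pneumonitis, or pembrolizumab after another immune-related event, when the event table says that treatment should end. Section 6.1.2 itself warns that drug-induced pneumonitis can be immediately life-threatening. What is at stake is patient safety and consistent dosing across sites.

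**Working it through.** The plan gives no combined figure to reproduce, so the check puts both clocks on one scale: days since the last dose.

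**Inputs.** Cycle length 21 days (Section 5.1). Delay limit 12 weeks (Section 6.3). Stop limit 12 weeks from last dose (Table 4 note 2, Table 7 instruction 2). Steroid taper over at least 4 weeks (28 days), begun at Grade 1 or lower (Table 4 note 1, Table 7 instruction 1).

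**Assumptions.** Delay is counted from the due date of the next cycle. Resolved means Grade 1 or lower. The ±3-day dosing window is ignored.

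**Step 1: the two limits.**
- Tables: 12 × 7 = day 84.
- Section 6.3: 21 + 12 × 7 = day 105 (15 weeks).
- Gap: 105 − 84 = 21 days.

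**Step 2: resolution limb, pneumonitis.** Let r be the day Grade 1 is reached.

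*Section 6.3 read alone, with no taper.* The delay is r − 21. For resolution at week 14, r = 98 and the delay is 98 − 21 = 77 days (11 weeks). The ordinary criteria are met without the waiver, yet 98 > 84, so Table 4 says stop. The same holds for r from 85 to 105.

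*With the 28-day taper applied.* The earliest resumption is r + 28, so the shortest delay is r + 28 − 21 = r + 7.

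| r (days) | Earliest resumption | Shortest delay | Tables | Section 6.3 |
|---|---|---|---|---|
| 77 | 77 + 28 = 105 | 84 days | met, if steroids are down in time | ordinary criteria |
| 78 to 84 | 106 to 112 | 85 to 91 days | met, if steroids are down in time | waiver needed, legitimately |
| 85 | 85 + 28 = 113 | 92 days | stop | only through the waiver |

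The route to conflict therefore depends on the reading: the ordinary criteria if Section 6.3 stands alone, the waiver only if the taper applies.

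**Step 3: steroid limb.** The tables tie resolution to the last dose but give no start point for the 12 weeks allowed for steroid reduction. Let s be the day that clock starts. The limit is s + 84, and the conflict window under the ordinary criteria runs from s + 85 to 105.
- s = 0 (last dose): limit day 84, window days 85 to 105.
- s = 7 (steroids begun on day 7): limit 7 + 84 = day 91, window days 92 to 105.
- s = 21 or later: limit 21 + 84 = day 105 or later, no window.

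Example: Grade 1 on day 42, minimum taper to 42 + 28 = day 70, 10 mg/day reached only on day 90, re-dosing on day 98. The delay is 98 − 21 = 77 days, inside the Section 6.3 limit. With s = 0, 90 > 84 and the table says stop. With s = 7, 90 ≤ 91 and the patient complies.

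**Step 4: the restart bullets side by side.** The first stops treatment on non-resolution. The second permits restart on non-resolution. They cannot both apply, and the second makes sense only without its negation.

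**The case against.** The strongest defence is that specific event rules govern and Section 6.3 is the general rule. Section 6.1.2 says to follow Table 4. Section 6.2 holds both agents under Table 7 whatever the attribution, and its first restart bullet is mandatory. Section 6.3 itself sends events attributable to one agent back to Sections 6.1 and 6.2. Its criteria are necessary conditions, and a patient whose drugs are permanently stopped has no delayed cycle. Grade 3 or 4 and recurrent Grade 2 pneumonitis end both drugs outright. Resumption after Grade 2 pneumonitis needs discussion with the Overall PI, and the waiver needs the Overall PI's agreement.

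Most of this stands and keeps the point narrow. It does not close the gap, because none of these passages limits the waiver. The cross-reference covers only events attributable to one agent, and Section 6.2 says such attribution is likely to be difficult.

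A reader might infer four stronger things that the documents do not support:
- *Section 6.3 has no time limit for pneumonitis.* Its pneumonitis bullet has none, but the general 12-week delay limit covers any treatment-related toxicity.
- *Nothing in the plan indicates which rule governs.* Several passages favour the tables; what is missing is a statement that reaches the waiver.
- *The steroid conflict always spans days 85 to 105.* That holds only if the clock starts at the last dose.
- *For Table 7 events only pembrolizumab is in question.* Instruction 2 names only pembrolizumab, but the first restart bullet covers all study drugs, while Section 6.3 lets a second agent resume.

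**Conclusion.** The point holds as a narrow inconsistency in the dosing rules, not a direct contradiction. Section 6.3 can be read to allow re-dosing that Table 4 note 2 or Table 7 instruction 2 rules out, because its limit falls about 21 days later, ignores steroid dose and can be waived without excluding any event. The day counts rest on the assumptions listed in the working and change with the reading of the taper and of the steroid clock.

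The number of patients is not given. It is confined to a first Grade 2 pneumonitis or a withheld Table 7 event that resolves late or tapers slowly, in a trial of at most 35. For rough scale, Table 8 lists pneumonitis of Grade 2 or lower in 34 of 404 mirvetuximab patients. If that rate applied here, 35 × 34/404 = 2.9, about 3 patients, would have the event, and fewer would reach the conflict. The rate is an assumption: it is not specific to this combination and says nothing about Table 7 events.

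This is a minor safety clarification worth making, with no effect on ORR, PFS6 or the error rates.

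**What to change.** Make three changes in one amendment.

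1. Add to Section 6.3: *Nothing in this section, including the clinical-benefit exception, permits re-dosing with an agent that Table 4 note 2 or Table 7 instruction 2 requires to be permanently discontinued, however the event is attributed.*
2. Delete the stray *not* in the second bullet of Section 6.2, Restarting Study Interventions.
3. Align *all study interventions* in the first bullet there with Table 7 instruction 2 (pembrolizumab only) and with Section 6.3 (the second agent may resume). Leave Table 4's rule for both agents in pneumonitis as it is.

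Keep the Section 6.3 delay limit for all toxicities. Keep the waiver for events that meet the tables, such as Grade 1 on days 78 to 84 followed by the 28-day taper. Keep the Table 7 note on endocrinopathy.

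The cost is a few lines of text, with no change to sample size, schedule or data collection. The downside is that a few benefiting patients with late-resolving immune-related events lose access to the waiver.
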